#### **4.3.1 Consent Description**

Informed consent will take place in the preoperative holding area the day of the scheduled procedure. The investigator will perform the informed consent process by re-explaining the study in detail, providing the ICF/HIPAA, and obtaining the subject's signature.

## **5.0 Study Design and Procedures**

### **5.1 Schedule of Events**

Not applicable.

#### **Legend**

- **R** = Research item/procedure done only for research purposes and their costs are covered by the study. You are not responsible for the costs of these procedures.
- **S** = Standard of care item/procedure that is part of regular care and billed to the patient/insurance. You and your insurance company will be responsible for these costs.
- **RB** = Research item/procedure that is related to use of the study device or administration and monitoring of study drug but billed to the patient/insurance. You and your insurance company will be responsible for these costs.
- **SS** = Standard of care item/procedure that is part of regular care but their costs are covered by the study. You are not responsible for the costs of these procedures.

Procedures	Visit #1
Demographic Information	S
Endoscopy	S
Informed Consent	R
Oxygenating Bite Block	R
Questionnaire	R

### **5.2 Study Design and Duration**

This a prospective, observational pilot study that aims to evaluate an Oxygenating Bite Block prototype in obese patients undergoing endoscopy. The endoscopy procedure nor the anesthesia management will change from current practices. The investigators will

hand out a short questionnaire to the patient, anesthesiologist, and endoscopist following the procedure regarding tolerability and/or feasibility of the device.

The duration of the study is about one day.

The study will be conducted on-site at Cedars-Sinai.

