## 2.0 Background, Rationale

Hypoxemia due to respiratory depression or airway obstruction is a known risk associated with endoscopic procedures, with studies showing that hypoxemia occurs in 11–50% of cases [1].

The current standard for oxygenating and monitoring a sedated patient for endoscopy has not evolved since the advent of capnography over 30 years ago. The procedure for sedation for upper endoscopy, ERCP and Transesophageal Echocardiography from an anesthetist's standpoint is as follows: A bite block is placed to protect the teeth and maintain oral latency for scope placement. A choice is then made to use either a face mask with a hole cut to pass the endoscope through, or to use a nasal cannula to oxygenate and monitor respirations. The face mask can easily be pushed into the patients' eyes inadvertently by the endoscopist creating a safety hazard, or the nasal cannula can be used which provides a lower fractional oxygen concentration.

This Oxygenating Bite Block (OBB) overcomes both problems and additionally it improves on both monitoring and oxygenating. The oxygen is delivered at the distal portion of the scope guide which reduces the anatomic dead space that the oxygen is required to overcome before reaching the lungs. Sedated patients loose muscle tone and have a reduced ability to ventilate their lungs with fresh air. The endoscopists often use CO2 to insufflate while they are examining the patient and the CO2 is 20x as diffusible as oxygen - requiring the O2 being delivered to overcome the diffusion gradient of CO2 coming from the esophagus. This reduction in dead space and improved oxygenation should make sedation safer. An additional improved safety aspect of this device is the integrated ETCO2 monitor which can be attached to a

capnography machine and monitor to ensure the sedated patient is breathing well. The ETCO2 is sampled from inside the mouth which is a more accurate sampling location. Additionally, sedation for endoscopies with propofol is increasingly being done by non-anesthetists. Propofol is a significant respiratory depressant, and the incidence of complications and hypoxemia is higher when the endoscopist uses propofol without an anesthetist present [2]. The oxygenating bite block is designed to improve oxygenation and monitoring in these situations.

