### **Differences between the OBB and the Oral Airway**

The conventionally used Anesthesia and sedation support device is known as an 'Oral Airway'. Our study device is called the OBB. Both the OBB and the Oral Airway are small disposable devices that go in the mouth with the same basic form and size. The OBB is an oral airway that delivers oxygen, ***thus eliminating the need for a separate oxygen delivery product*** like a nasal cannula or face mask. The OBB delivers oxygen closer to the glottic opening in the retro pharynx, thus eliminating 'dead space'. Dead space is a space where Oxygen/CO2 exchange does not occur.

Additionally, the OBB has an OS (or 'mouth' of the device) where an endoscope can be placed and the ETCO2 sampling occurs via tubing attached to the device. This allows ETCO2 sampling to improve safety for sedated patients. By oxygenating and monitoring ETCO2, the OBB is just an advanced and safer oral airway. This novel device is not sufficiently different in dimensions or use than currently existing technology.

The OBB has a slightly thinner flange than the Oral Airway and a larger opening at the mouth which is identical to the existing bite blocks currently in use. This larger opening will allow the OBB to be used during endoscopy sedation. The commonly used 'Oral Airway' cannot be used during endoscopy sedation due to the thickness of the flange and the limited space between the teeth, which prevents passage of an endoscope.

The Oxygenating Bite Block (OBB) we are using for this study does not hold FDA 510k clearance, therefore this device would be categorized as an investigational, non-significant risk device due to the following reasons:

- Is NOT intended as an implant and does NOT present a potential for serious risk to the health, safety, or welfare of a subject.
- Is NOT purported or represented to be for use supporting or sustaining human life and does NOT present a potential for serious risk to the health, safety, or welfare of a subject;
- Is NOT for a use of substantial importance in diagnosing, curing, mitigating, or treating disease, or otherwise preventing impairment of human health and does NOT present a potential for serious risk to the health, safety, or welfare of a subject; or
- Does NOT otherwise present a potential for serious risk to the health, safety, or welfare of a subject.

- Does NOT meet device exemption criteria.

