### 3.0 Study Purpose and Objectives

The primary objectives of this study are:

- 1) To evaluate the tolerability and efficacy of the Oxygenating Bite Block during sedation for endoscopic procedures.
- 2) To evaluate the Oxygenating Bite Block from the endoscopist and anesthesiologist perspective. These professionals will be part of the study team.

The secondary objectives of this study are:

- 1) To collect preliminary answers regarding the physician and patient tolerability and feasibility of the OBB through questionnaires.

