### **5.3 Description of Study Procedures**

The study involves participation at a single timepoint only. The study procedures to be done are listed below.

The only data to be collected are three questionnaires. Following the procedure, the patient, anesthesiologist, and gastroenterologist will be given a short questionnaire administered in-person regarding the tolerability and feasibility of the OBB.

The following will be collected and analyzed from the patient questionnaire:

- 1) Satisfaction of sedation level during the procedure
- 2) Tolerability of the OBB
- 3) Presence of a sore throat

The following will be collected and analyzed from the anesthesiologist questionnaire:

- 1) Ease of use of the OBB
- 2) Adequacy of teeth protection
- 3) Efficacy of oxygenation of the OBB
- 4) Efficacy of oxygenation in comparison with currently available alternatives for MAC
- 5) Efficacy of ETCO2 monitoring
- 6) Potential future use of the OBB
- 7) Desaturation of patient
- 8) Professional opinion of the OBB

The following will be collected and analyzed from the gastroenterologist questionnaire:

- 1) Patient tolerability of the OBB
- 2) Potential future use of the OBB
- 3) Interference of the OBB with endoscopy performance
- 4) Professional opinion of the OBB

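### A 'no desaturation' answer cannot be credited to the OBB, because nothing listed records other oxygen use or whether the OBB stayed in place

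*Combined protocol and SAP*

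**What the plan says.** - **Objective.** The first primary objective in section 3.0 is "To evaluate the tolerability and efficacy of the Oxygenating Bite Block during sedation for endoscopic procedures".
- **Role of the device.** Section 2.0 describes usual care as a bite block with either a face mask that has a hole cut for the endoscope, "or to use a nasal cannula to oxygenate and monitor respirations". After listing the drawbacks of each, it says "This Oxygenating Bite Block (OBB) overcomes both problems". The subsection comparing the OBB with the oral airway adds that it delivers oxygen itself, "thus eliminating the need for a separate oxygen delivery product".
- **Conduct.** Section 5.2 states "The endoscopy procedure nor the anesthesia management will change from current practices". No section says whether a mask or cannula may be used with the OBB.
- **Data.** Section 5.3 says "The only data to be collected are three questionnaires". The anesthesiologist's topics include OBB oxygenation efficacy (item 3), "Efficacy of oxygenation in comparison with currently available alternatives for MAC" (item 4) and desaturation (item 7). Section 6.3 adds only diagnosis and date of treatment.
- **Other sources.** Section 6.1 says that medical record data will not be accessed. Section 7.1 sends adverse events and deviations to the IRB. Section 8.3 takes the outcome data from the three questionnaires and summarises them as frequencies and percentages.

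**The concern.** Item 7 is the listed topic closest to an objective oxygenation outcome. A reader will take a low desaturation percentage as evidence that the OBB oxygenates sedated patients adequately. That holds only if the OBB was the oxygen source and was in place during the period described.

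The plan leaves both conditions open. The background suggests that the OBB replaces the mask or cannula, while 5.2 can be read as allowing them to continue. If an anesthesiologist keeps a cannula running, adds oxygen as a precaution, or takes the OBB out before saturation falls, the form can truthfully show no desaturation. The result then describes the OBB plus something else, or something else alone. With records excluded, the plan offers no way to sort this out afterwards.

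**Working it through.** There is no calculation in the plan to reproduce: 8.1 fixes the sample at 10, and 8.2 says that a pilot of at most 20 needs no justification. The check is therefore mainly a reading of what is captured.

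**Step 1: is other oxygen or OBB removal listed anywhere?** The topics in 5.3 number 3 (patient) + 8 (anesthesiologist) + 4 (gastroenterologist) = 15. None names concurrent oxygen, rescue oxygen or early removal. Nor does 6.3. Section 6.1 contains general bullets about access to clinical data sources, but its specific statement excludes medical record data. Under 7.1 a deviation would reach the IRB; with no rule on other oxygen, using it would not be a deviation, and IRB reports are not outcome data under 8.3.

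**Step 2: which courses of events can be told apart?**

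| What happened | Item 7 answer | Separable from the listed topics? |
|---|---|---|
| OBB alone, in place to the end, no fall in saturation | No desaturation | Reference case |
| Mask or cannula from the start, no fall | No desaturation | No |
| Oxygen added, or OBB removed, before any fall | No desaturation | No |
| Saturation falls, then rescue | Desaturation | Event is captured; the rescue is not |

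The second and third rows are the problem. The fourth is not, provided item 7 counts events that were later corrected; nothing in the documents says otherwise.

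**Step 3: how large can the effect be?** Input: N = 10 (8.1). One patient shifts the percentage by 1/10 = 10 points, whatever the starting count: 1/10 (10%) would become 2/10 (20%), and 5/10 (50%) would become 6/10 (60%).

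Suppose the report is 0/10 and k of the 10 patients belong to the second or third row. The count on the OBB alone could then lie anywhere from 0/10 (none of the k would have desaturated) to k/10 (all would have). The values of k are assumptions, because the documents give none:

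| k (assumed) | Reported | Possible on OBB alone |
|---|---|---|
| 0 | 0% | 0% |
| 1 | 0% | 0 to 10% |
| 2 | 0% | 0 to 20% |
| 3 | 0% | 0 to 30% |
| 5 | 0% | 0 to 50% |

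As planned, all five rows produce the same report. Recording k would show which row applies.

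**The case against.** The strongest case against the point has five parts.

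1. **Rescue usually follows a desaturation.** Correct. A reader might infer that any rescue mask hides a device failure. It does not: oxygen given because saturation fell comes after an event that item 7 covers. Only oxygen from the start, or oxygen or removal ahead of a fall, masks anything.
2. **Concurrent use is not stated.** Also correct. A reader might infer from 5.2 that a mask or cannula will be used with the OBB. The sentence names neither and may mean only that sedation care is unchanged, and section 2.0 points toward the OBB as sole source. The documents leave the matter open; that is an ambiguity, not evidence of concurrent use.
3. **The forms are not shown.** Section 5.3 gives topics, not questions. Ease of use or professional opinion might draw a comment about other oxygen or removal. What can be said is that no listed topic requires it.
4. **Failure can surface elsewhere.** The anesthesiologist knows what was in use, and items 3, 4, 6 and 8 can reflect a disappointing device. They are not masked in the same way as item 7, but they cannot be read against the oxygen actually delivered.
5. **Ten patients are imprecise anyway.** For 0/10 the exact 95% upper limit is 1 − 0.025^(1/10) = 30.8%, so a one-patient shift lies inside the sampling uncertainty. That limit describes chance variation around a known treatment. It does not say which oxygen source produced the result, and that is the missing information.

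The first three objections narrow the point. The last two limit its weight but leave the gap in place.

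**Conclusion.** The point stands in a limited form. Oxygenation efficacy belongs to the first primary objective, yet following the plan as written can yield a 'no desaturation' result that cannot be attributed to the OBB and, with records excluded, cannot be clarified later. The size is 10 percentage points per affected patient.

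How many patients would be affected is not in the documents. A reader might be tempted to estimate it from section 2.0, which says hypoxemia "is a known risk associated with endoscopic procedures, with studies showing that hypoxemia occurs in" 11–50% of cases. That range concerns endoscopy generally, not the OBB, and says nothing about how often other oxygen would prevent a recorded fall. Any probability built on it would only reflect the share assumed.

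Nor do the documents support the inference that the efficacy evaluation as a whole is invalid. No test, error rate or formal comparison is planned, desaturation is one of 15 topics, and the effect is on descriptive interpretation of a 10-patient pilot. The conclusion rests on the topic list in 5.3 being a fair guide to the forms. If the forms already ask about other oxygen and removal, only the reporting line and the clarification in 5.2 remain to be added.

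**What to change.** **Anesthesiologist form.** Add two tick-box items if they are not already there:
- other oxygen used: none / from the start / added before desaturation / added after desaturation;
- OBB in place to the end of the procedure: yes / no, with reason.

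**Section 8.3.** Report these counts beside the desaturation and oxygenation-efficacy percentages, for all patients in whom OBB placement was attempted, without dropping any.

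**Section 5.2.** State whether the OBB is intended as the sole or a concurrent oxygen source, and make the sentence on unchanged management agree. Sole-source use need not be mandated; doing so could itself change care in a study described as observational. Recording what happened is enough.

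**Cost.** A slightly longer form, a sentence or two of protocol text, and a result that may look less favourable. No extra patients, visits or record access are needed.

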### **5.3 Description of Study Procedures**

The study involves participation at a single timepoint only. The study procedures to be done are listed below.

The only data to be collected are three questionnaires. Following the procedure, the patient, anesthesiologist, and gastroenterologist will be given a short questionnaire administered in-person regarding the tolerability and feasibility of the OBB.

The following will be collected and analyzed from the patient questionnaire:

- 1) Satisfaction of sedation level during the procedure
- 2) Tolerability of the OBB
- 3) Presence of a sore throat

The following will be collected and analyzed from the anesthesiologist questionnaire:

- 1) Ease of use of the OBB
- 2) Adequacy of teeth protection
- 3) Efficacy of oxygenation of the OBB
- 4) Efficacy of oxygenation in comparison with currently available alternatives for MAC
- 5) Efficacy of ETCO2 monitoring
- 6) Potential future use of the OBB
- 7) Desaturation of patient
- 8) Professional opinion of the OBB

The following will be collected and analyzed from the gastroenterologist questionnaire:

- 1) Patient tolerability of the OBB
- 2) Potential future use of the OBB
- 3) Interference of the OBB with endoscopy performance
- 4) Professional opinion of the OBB

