## 7.0 Data and Safety Monitoring

### 7.1 Data and Safety Monitoring Plan

The study will be monitored by the PI to ensure appropriate study conduct, including obtaining proper access to data/specimens, compliance with the HIPAA Privacy Rule, compliance with Cedars-Sinai policy, and adhering to the plans outlined in the protocol for all study procedures, abstracting and recording data, data and/or specimen security and maintenance, and data accuracy and integrity. Any adverse events, deviations, protocol exception requests, potential unanticipated problems involving risks to subjects or others, or other events will be submitted to the IRB in accordance with [IRB reporting policy](#). All study procedures will be conducted in accordance with standard clinical practice.

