## 8.0 Sample Size and Statistical Considerations

### 8.1 Sample Size

This is a single on-site study at Cedars-Sinai. The sample size of the study is 10 subjects.

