### 8.2 Statistical Sample Size Justification

A statistical sample size is not required because this study involves:

- A pilot study with at most 20 subjects

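### Apart from sore throat and desaturation, no listed questionnaire item records device injury, bleeding, dislodgement or malfunction as an event, and adverse events sent to the IRB are not in the planned outcome data

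*Combined protocol and SAP*

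**What the plan says.** - **Objective.** Section 3.0 gives as the first primary objective: "To evaluate the tolerability and efficacy of the Oxygenating Bite Block during sedation for endoscopic procedures".
- **Device.** Section 5.2 says the study "aims to evaluate an Oxygenating Bite Block prototype in obese patients undergoing endoscopy". The background section on how the device differs from an oral airway adds: "The Oxygenating Bite Block (OBB) we are using for this study does not hold FDA 510k clearance".
- **Data.** Section 5.3 says: "The only data to be collected are three questionnaires". It lists 3 patient items, 8 anesthesiologist items and 4 gastroenterologist items. Section 6.3 adds only diagnosis and treatment date, and neither is a harm. Under data sources, section 6.1 says that medical records will not be used. Section 6.2 limits collection to the day of the procedure.
- **Adverse events.** Section 7.1 covers "Any adverse events, deviations, protocol exception requests" and similar occurrences, which go to the IRB under its reporting policy. It gives no method of asking, no definition and no form.
- **Analysis.** Section 8.3 takes the outcome data from the three questionnaires and summarises them as counts and percentages. It plans no adverse event summary.
- **Size.** Section 8.1: "The sample size of the study is 10 subjects".

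**The concern.** A tolerability conclusion depends on which harms were looked for. The events one would most want to count for a new device held between the teeth are a chipped tooth, a cut lip or tongue, bleeding, the device coming out or being taken out, and a failed oxygen or sampling line. None is a listed item.

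The protocol itself treats the mouth and jaw as the area at risk. Section 4.2 excludes patients with absent or mobile front teeth, jaw-joint disease or facial deformity. The plan thus screens for vulnerability to this kind of injury, but lists no item that records the injury itself.

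At stake is how a favourable result can be read. If the report says the device was well tolerated, a reader could not tell whether these events did not occur or were not asked about. A signal that should shape the next study could be lost.

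**Working it through.** **1. Figure to reproduce.** There is none. Section 8.2 justifies the sample size only as "A pilot study with at most 20 subjects", with no rate, precision or power. The check is therefore mainly one of content.

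**2. Item count (section 5.3).** 3 + 8 + 4 = 15 items.
- Items that name a harm event: sore throat (patient) and desaturation (anesthesiologist), 2 of 15.
- Items that name oral or dental injury, bleeding, dislodgement or removal, or malfunction as an event: 0 of 15.

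**3. Nearest listed item for each missing event.**

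| Event | Nearest listed item | Does it identify the event? |
|---|---|---|
| Tooth injury | "Adequacy of teeth protection" (anesthesiologist) | No. It asks about protection. A low rating does not show an injury and a high one does not exclude it. |
| Lip, tongue or mucosal injury; bleeding | Tolerability (patient, gastroenterologist) | No. It may lower the rating, but the cause is not recorded. |
| Device dislodged, removed or replaced | Interference with the endoscopy (gastroenterologist); ease of use (anesthesiologist) | No. It is a partial proxy. |
| Oxygen or sampling line malfunction | Efficacy of oxygenation and of ETCO2 monitoring (anesthesiologist) | No. Poor performance and a failed part look the same. |

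**4. Other routes into the results.** Medical records are ruled out in 6.1. That section also carries a general line about study-team access to clinical data, which reads like one of several form options; the specific statement on data sources excludes it. Section 7.1 sends adverse events to the IRB, but 8.3 does not bring them back into the outcome data.

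**5. Illustration of size.** The documents give no rate for these events, so the true rate p is assumed and shown as a range. With n = 10 from section 8.1 and every case asked about, the chance of recording at least one case is 1 − (1 − p)^10:
- p = 5%: 1 − 0.95^10 = 0.401
- p = 10%: 1 − 0.90^10 = 0.651
- p = 20%: 1 − 0.80^10 = 0.893

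If 0 of 10 are recorded with full prompting, the exact two-sided 95% upper limit is 1 − 0.025^(1/10) = 0.308.

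If an event has no item and nobody volunteers it, the recorded count is zero at any true rate, and no upper limit can be given. The plan as written lies somewhere between that case and full prompting. The documents do not allow the point to be fixed.

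**The case against.** The best defence has four parts.

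- **Harms are asked about.** Sore throat and desaturation are listed, so a reader who inferred that the study asks about no harms would be wrong. This stands, and it limits the point to the events named above.
- **The ratings would react.** A painful lip or visible bleeding can lower a tolerability rating, a chipped tooth can lower the teeth-protection rating, and a failed line can lower the oxygenation or ETCO2 rating. A reader might infer that such events cannot enter the tolerability result at all. The listed items do not support so absolute a claim. What remains is that the events would not be identifiable or countable.
- **The forms are not in the documents.** Section 5.3 lists topics, not wording or response formats. The clinicians' general-opinion items, for example, could include free text. So one can say that no listed item records these events, but not that no form does. Free text would still be unprompted and would not give a reliable count per patient.
- **Witnesses are inside the reporting chain.** Section 3.0 makes the endoscopist and anesthesiologist members of the study team, and 7.1 sends any adverse event to the IRB. Visible events may well be reported. The exclusions in 4.2 should also lower the dental and jaw risk. Both points stand, and they are reasons not to put a figure on the shortfall. Neither gives these events a place in the 8.3 results.

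It is also fair to say that this is a descriptive pilot of 10 patients with no test or decision threshold.

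**Conclusion.** The point holds in a limited form. For a primary objective on an uncleared prototype, 0 of 15 listed items record oral or dental injury, bleeding, dislodgement or removal, or malfunction as an event. The planned outcome data have no other source for them. Such events need not appear in the results, although related ratings may partly reflect them.

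The documents do not show that the tolerability result will be falsely favourable, or by how much. That would need both an event rate and the share of events reported unprompted, and neither is given. The 40%, 65% and 89% figures rest on assumed rates of 5%, 10% and 20%, independent patients and complete prompting. They show what asking could deliver, not what the present plan loses.

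Nor would asking settle safety: 0/10 remains compatible with a true rate of up to 31%. The gain is that a zero would then mean the question was asked. I would treat this as a cheap improvement. It does not make the pilot unsound.

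**What to change.** **Section 5.3, anesthesiologist and gastroenterologist forms.** Add yes/no items:
- tooth, lip, tongue or mucosal injury;
- bleeding;
- device dislodged, removed or replaced;
- oxygen or sampling line malfunction.

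**Section 5.3, patient form.** Add one yes/no item: mouth, tooth or jaw pain.

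**Section 8.3.** Report each item as a count over all patients in whom placement of the device was attempted, so that failed placements stay visible. List any adverse event sent to the IRB alongside. Where 0 of 10 is observed, give the exact upper limit so that it is not read as proof of safety.

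**Cost.** About five tick boxes on forms already completed the same day, and a line or two in 8.3. The forms become slightly longer, and some minor events will be reported that would otherwise go unmentioned. No extra staff, procedure, patients or record access is needed.

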## **6.0 Data Collection and Management**

### **6.1 Data Procurement**

- **Identification/Access/Abstraction**

- Members of the study team will require access to the clinical data source (e.g., electronic medical record) to identify eligible data/specimens and to conduct data abstraction or gain access to specimens.
- Separate registry or repository will identify, abstract, and/or provide specimens and/or data to the study team.
- Other:

Data will be collected directly from the patient, anesthesiologist and endoscopist using a questionnaire and no identification will be included.

- **Source(s) of Data/Specimens:**

No medical record data will be accessed as part of this research.  
All data is collected from the questionnaire for the patient, questionnaire for the anesthesiologist, and questionnaire for the gastroenterologist.

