### 8.3 Statistical Analysis Methodologies

This pilot study will obtain *response rates*. The questionnaire for the patient, questionnaire for the anesthesiologist, and questionnaire for the gastroenterologist for this research study, will be collated and reviewed by the investigator to provide the outcome data. We will use *frequencies and percentages and the similar responses will be compared across the 3 questionnaires applied*.

No statistical methods description is required given that the study does not require a sample size justification.

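### The patient questionnaire is given in person by the investigators, who also take consent and review the answers, so patient ratings of the device may lean favourable; private completion and sealed return would reduce this at little cost

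*Combined protocol and SAP*

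**What the plan says.** Section 5.2 has the investigators "hand out a short questionnaire to the patient, anesthesiologist, and endoscopist following the procedure". Section 5.3 adds that the three respondents "will be given a short questionnaire administered in-person regarding the tolerability and feasibility of the OBB". Neither section says whether the patient fills in the form alone, whether an investigator is present, or how the form is returned.

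Other sections fill in the setting:

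- Recruitment (4.3): the endoscopist or anesthesiologist gives the patient the invitation letter and explains the study. Section 3.0 says of these clinicians: "These professionals will be part of the study team".
- Consent (4.3.1): an investigator obtains it on the day of the procedure.
- Review (8.3): the completed forms are collated and "reviewed by the investigator to provide the outcome data". The analysis is frequencies and percentages, with similar responses compared across the three forms.
- Data sources: "The only data to be collected are three questionnaires" (5.3) and "No medical record data will be accessed as part of this research" (6.1).
- Anonymity: data are collected "using a questionnaire and no identification will be included" (6.1), while diagnosis and date of treatment are listed as data elements (6.3).
- Size: 10 subjects in a single group (8.1).

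**The concern.** Two of the three patient items, satisfaction with sedation and tolerability of the device, are matters of opinion. The third, sore throat, is a symptom report. The patient has been invited, consented and treated by the study team that day, then receives the form from an investigator in person. Some patients in that position give a kinder answer than they would in private.

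Tolerability is part of the first primary objective (3.0), and the patient form is the only place where patients speak for themselves. There is no control group whose ratings would carry the same bias, and no record data to check answers against. A favourable shift would pass unseen into the reported percentages.

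**Working it through.** The plan gives no calculation to reproduce: 8.1 states 10 subjects, and 8.2 says that no justification is required. The check is therefore a reading of the passages, followed by an illustration of scale.

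**Contact between patient and study team**

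| Step | Who | Section |
|---|---|---|
| Invitation | Endoscopist or anesthesiologist, both part of the study team | 4.3, 3.0 |
| Consent | Investigator | 4.3.1 |
| Handing out the form | Investigators | 5.2 |
| Mode | In person, after the procedure | 5.3 |
| Collation and review | Investigator | 8.3 |

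Every step sits with the study team. The documents do not say that one individual does all of them, and no step describes privacy.

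**Strength of the anonymity safeguard**

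A form without a name protects the patient only if the reader cannot tell whose it is. Here there are 10 patients at one site, forms pass from hand to hand on the day of the procedure, and date of treatment is a listed data element. The protocol does not say whether the date is written on the form. An investigator could often recognise the respondent either way.

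**Scale of one changed answer**

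With all 10 patients answering, one answer is 1/10 = 10 percentage points. With fewer respondents it is more.

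**Illustration over a range**

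The documents give neither of the following inputs, so both are assumptions: *p*, the true favourable rate on a patient item, and *b*, the share of unfavourable raters who answer favourably because of the setting. The expected observed rate is *q* = *p* + (1 − *p*)*b*. The chance of at least 8 favourable answers in 10 is the upper tail of a binomial(10, *q*). Eight is an arbitrary marker; the plan sets no threshold.

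| *p* | *b* | *q* | Chance of at least 8/10 |
|---|---|---|---|
| 0.60 | 0 | 0.60 | 0.17 |
| 0.60 | 0.10 | 0.64 | 0.24 |
| 0.60 | 0.25 | 0.70 | 0.38 |
| 0.60 | 0.50 | 0.80 | 0.68 |
| 0.80 | 0 | 0.80 | 0.68 |
| 0.80 | 0.10 | 0.82 | 0.74 |
| 0.80 | 0.25 | 0.85 | 0.82 |
| 0.80 | 0.50 | 0.90 | 0.93 |

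For example, 0.60 + 0.40 × 0.25 = 0.70. For comparison, the exact (Clopper-Pearson) 95% interval is 26.2% to 87.8% for 6/10 and 44.4% to 97.5% for 8/10. Sampling error alone is therefore large. The difference is that the setting would push in one direction, and an interval does not show that.

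**Where the items come from**

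Section 5.3 lists 3 patient, 8 anesthesiologist and 4 gastroenterologist items. So 3 of 15 come from patients and 12 of 15 from clinicians who belong to the study team.

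**The case against.** A reader might infer that patients and clinicians answer in front of the people testing the device. The documents do not say so. Handing out a form is compatible with private self-completion, and the in-person wording permits an observer without requiring one. This objection stands: the bias is possible, not shown. The wording still leaves the more exposed procedure open when a sentence would close it.

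The forms carry no identification. This is a real safeguard, but a weak one for the reasons given above.

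Most items are answered by clinicians on the study team. Their interest in the result exists however the form is handed over, and an envelope does not cure it. This stands in full, so the bias argument here is confined to the three patient items. What can be improved on the clinician side is independence. Section 8.3 compares responses across forms, and both the patient and the gastroenterologist are asked about tolerability. Agreement means less if the raters have conferred. The documents do not say that they do, but nothing prevents it.

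It would also go too far to say that every outcome is opinion and every percentage would shift. Desaturation is an observable event, although it is reported by questionnaire, and sore throat is a symptom. The item wording is not in the documents.

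Finally, this is a descriptive pilot with no test or decision rule, so no stated conclusion can be shown to change. That limits the weight of the point. It is not a reason to keep an avoidable source of bias.

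**Conclusion.** The concern holds for the patient form. Investigators give it out in person, an investigator also takes consent and reviews the answers, and no private completion or sealed return is provided. Patient ratings may therefore be biased toward favourable.

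Neither the presence nor the size of a shift can be established from the documents. The only figure that follows from the plan is 10 percentage points per changed answer, assuming that all 10 patients respond. The illustrative rates rest on assumed values of *p* and *b*, and they include no shift at all.

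The documents do not support the stronger conclusions that raters are observed while answering, that answers are in fact pushed upward, or that a change of mode would make the clinician ratings impartial. The point is a cheap improvement to the procedure and does not invalidate the pilot.

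**What to change.** Amend 5.2 and 5.3 as follows:

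1. **Patient form.** Replace in-person administration with self-completion on the same day, with no investigator or treating clinician present. The form bears no name and is returned in a sealed envelope.
2. **Clinician forms.** The anesthesiologist and gastroenterologist each complete their form independently, before seeing or discussing the other answers.
3. **Linkage.** If a code is needed to link the three forms, use a random one and reconcile it with the statement in 6.1 that no identification is included.
4. **Safety.** State that adverse events are reported under 7.1 independently of the questionnaires. Do not hold the envelopes until the tenth patient: the forms are the only study data and include desaturation and sore throat, so sealing them could delay the principal investigator's monitoring.
5. **Reporting.** State that the clinician raters belong to the study team, and that this change does not remove that conflict.

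The cost is envelopes and a few sentences of protocol text, with no extra patients, visits or staff. The downside is that unclear items cannot be clarified on the spot, so a few more may be blank or ambiguous. With 10 patients, the number answering each item should be reported beside its percentage.
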